#### 6.4.6 Supportive Care

Patients should receive appropriate supportive care measures as deemed necessary by the treating medical oncologist. Supportive care measures for the management of AEs with potential immunologic etiology are provided in the prescribing information for the specific PD-1 or PD-L1 inhibitor.

### 6.5 Prohibited Medications and Treatments

#### 6.5.1 Cancer Treatment

Once study therapy is initiated, cancer treatment (eg, chemotherapy, biological therapy, immunotherapy, RT) other than the treatment specified in the protocol for this study is not permitted until disease progression. Continuation of hormonal anti-cancer therapy is permitted at investigator discretion. Steroids for CNS edema management are considered supportive care, not anti-cancer treatment.

### 6.5.2 Other Medications

- Live vaccines (examples of live vaccines include, but are not limited to, the following: measles, mumps, rubella, varicella/zoster, yellow fever, rabies, BCG, and typhoid vaccine) are prohibited.
- Administration of investigational agents is not permitted until disease progression (see Section [5.2](#) regarding study withdrawal).

### 6.5.3 Concurrent Medications

Concurrent medications will be recorded in source documents at visits in accordance with the study calendar. The only concurrent medications required to be captured in eCRFs are:

- Oral or parenteral steroids
- Any immunotherapy given other than PD-1 or PD-L1 inhibitor (see Section [4.2.1](#))
- Any hormonal therapy being used for cancer control (see Section [4.2.1](#))
- Any prohibited medication (see Sections 6.5.1 and 6.5.2)

## 6.6 Duration of Therapy

Study treatment will be administered as described in Sections [6.3](#) and [6.4](#) unless one of the following occurs (also see study withdrawal criteria in Section [5.2](#)):

- AE that requires discontinuation of study treatment
- Pregnancy
- Determination by the investigator that discontinuation is in the patient's best medical interest
- Patient decision to discontinue study treatment
- Withdrawal of study sponsor support

The reason for discontinuation of study treatment must be documented in the source documents and in the OnCore database.

## 6.7 Follow-Up Period

### 6.7.1 For AE Evaluation and Reporting

#### 6.7.1.1 AEs Related to SRT and/or PD-1 or PD-L1 Inhibiting Therapy

Assessment and reporting for all  $\geq$  grade 3 AEs will continue through 8 weeks following the last SRT fraction (Section [8.5.1](#)).

#### 6.7.1.2 AEs Related to PD-1 or PD-L1 Inhibiting Therapy

Assessment and reporting of selected AEs related to the PD-1 or PD-L1 inhibiting therapy as described in Section [8.5.2](#) will continue until the PD-1 or

PD-L1 inhibitor has been discontinued (for any reason) or until 2 years after completion of SRT, whichever occurs first.

#### 6.7.2 Follow-up for Treatment Response and Survival

Patients who remain on study will be assessed according to the study calendar ([Table 5](#)) through 2 years after completion of SRT.

## 7 DOSING DELAYS/DOSING MODIFICATIONS

### 7.1 SRT

There are no study-specified requirements for modification in the SRT treatment plan. However, the treating radiation oncologist may modify the fraction dose and/or schedule if necessary for patient safety.

### 7.2 PD-1 or PD-L1 Inhibitor

Dose reductions and/or treatment delays due to immune-related side effects of the PD-1 or PD-L1 inhibitor will be permitted at the discretion of the treating medical oncologist. The instructions for dosing delays and/or modifications provided in the prescribing information for the specific PD-1 or PD-L1 inhibitor can be referred to in making treatment modification decisions.

## 8 ADVERSE EVENTS: DEFINITIONS AND REPORTING REQUIREMENTS

### 8.1 Definitions

#### 8.1.1 Adverse Event (AE)

AE means any untoward medical occurrence associated with the use of a drug in humans, whether or not considered drug related.

#### 8.1.2 Serious AE (SAE)

An AE is considered “serious” if, in the view of either the investigator or sponsor, it results in any of the following outcomes:

- death,
- a life-threatening AE,

An AE is considered to be “life-threatening” if, in the view of either the investigator or sponsor, its occurrence places the patient at immediate risk of death. It does not include an AE that, had it occurred in a more severe form, might have caused death.

- inpatient hospitalization or prolongation of existing hospitalization,

Planned inpatient hospitalizations, eg, for planned surgery, or those that occur for logistical reasons, eg, to complete a therapy that cannot be completed due to outpatient clinic business hours, are exempt from SAE reporting. Events that

prolong such hospitalizations and otherwise meet reporting criteria are, however, still subject to SAE reporting requirements.

- a persistent or significant incapacity or substantial disruption of the ability to conduct normal life functions, or
- a congenital anomaly/birth defect.

Important medical events that may not result in death, be life-threatening, or require hospitalization may be considered serious when, based upon appropriate medical judgement, they may jeopardize the patient and may require medical or surgical intervention to prevent one of the outcomes listed in this definition.

### 8.1.3 Unanticipated Problem

An unanticipated problem (UP) includes any incident, experience, or outcome that meets all of the following criteria:

- unexpected (in terms of nature, severity, frequency) given (a) the research procedures that are described in the protocol-related documents, such as the research protocol and informed consent document approved by the institutional review board (IRB); and (b) the characteristics of the patient population being studied;
- related or possibly related to participation in the research (possibly related means there is a reasonable possibility that the incident, experience, or outcome may have been caused by the procedures involved in the research); and
- suggests that the research places patients or others at a greater risk of harm (including physical, psychological, economic, or social harm) than was previously known or recognized.

### 8.1.4 AE Description and Grade

The descriptions and grading scales found in the revised CTCAE v5.0 will be utilized for AE reporting.

### 8.1.5 AE Expectedness

AEs can be 'Unexpected' or 'Expected'.

- Expected AEs are those AEs, the specificity and severity of which, are listed or described in the current version of the FDA-approved prescribing information for the specific PD-1 or PD-2 inhibitor.
- Unexpected AEs are those AEs occurring in one or more patients participating in the study, the nature, severity, or frequency of which is not consistent with either:
  - The known or foreseeable risk of AEs associated with the procedures involved in the research that are described in (a) the protocol-related document, such as the IRB-approved research protocol and the current IRB-approved informed consent document, and (b) the FDA-approved prescribing information.
  - The expected natural progression of any underlying disease, disorder, or condition of the patient(s) experiencing the AE and the patient's predisposing risk factor profile for the AE.

### 8.1.6 AE Attribution

- Definite – The AE *is clearly related* to the study treatment.
- Probable – The AE *is likely related* to the study treatment.
- Possible – The AE *may be related* to the study treatment.
- Unlikely – The AE *is doubtfully related* to the study treatment.
- Unrelated – The AE *is clearly NOT related* to the study treatment.

## 8.2 Known AEs Associated with Stereotactic Radiotherapy

Fatigue is likely to occur for all treatment locations with an expected duration of < 8 weeks. Other AEs related to SRT for the treatment of metastases depend on the location of the lesions treated and exposure of surrounding normal tissues. The following list contains examples of possible SRT-related AEs but is not all-inclusive, given the diversity of sites that may be irradiated in this trial.

### 8.2.1 Lung (Central and Peripheral), Mediastinal/Cervical Lymph Node Metastases

- Cardiac and pericardial injury  
Cardiac and pericardial injury is uncommon in the conventionally-fractionated course of RT, side effects can be seen with large doses per fraction of SRT.
- Gastrointestinal/Esophageal injury  
Esophagitis (ie, dysphagia causing pain on swallowing) relatively soon after SRT is completed; typically resolves on its own within days to a week or longer
- Central Airway/Bronchial injury  
Bronchial toxicity includes:
  - Cough
  - Dyspnea
  - Hypoxia
  - Pleural effusion
  - Pleuritic pain associated with collapse
  - Bronchial necrosis/fistula
  - Hemoptysis/pulmonary hemorrhage
- Lung injury  
Radiation pneumonitis (ie, inflammation of the end bronchioles and alveoli); toxicities include:
  - Fever
  - Shortness of breath
  - Pulmonary infiltrate on chest x-ray

### 8.2.2 Liver/Abdominal-Pelvic Metastases

- Skin irritation, redness, itchiness, discomfort
- Asymptomatic decrease in blood counts
- Asymptomatic increase in liver enzymes
- Nausea and vomiting
- Gastric, esophageal, small bowel or large bowel irritation, ulceration, and/or bleeding
- Fistula
- Obstruction or changes in motility following therapy
- Chest wall pain
- Radiation-induced liver disease (RILD)
  - Classic RILD: Anicteric ascites, hepatomegaly, and elevation of alkaline phosphatase relative to other transaminases that may occur following SRT to the liver
  - Non-classic RILD: Elevation of liver enzymes and/or any decline in liver function
- Liver failure
- Permanent thrombocytopenia
- Bleeding

#### 8.2.3 Spinal Metastases

- Radiation myelitis
- Radiation esophagitis
- Radiation laryngitis or pharyngitis
- Radiation pneumonitis

#### 8.2.4 Osseous

- Erythema
- Desquamation
- Pain
- Edema
- Neuralgia

#### 8.2.5 Brain

- Nausea/vomiting
- Seizure
- Headache

### 8.3 Known AEs Associated with PD-1 or PD-L1 Inhibiting Therapy

Refer to the current prescribing information for the known AEs associated with the PD-1 or PD-L1 inhibitor the patient is receiving.

### 8.4 Secondary Malignancy

A secondary malignancy is a new cancer caused by previous treatment for a malignancy, eg, chemotherapy or RT. Metastatic disease is not a secondary malignancy. Any secondary malignancy should be reported via expedited reporting mechanisms.

### 8.5 Time Period and Grade of AE Capture

#### 8.5.1 From Initiation of SRT Until 8 Weeks Post-SRT

All SRT-related and immunotherapy-related **≥ grade 3** AEs will be recorded beginning at the time of the first SRT fraction and continuing until 8 weeks following completion of SRT.

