### 3.4 Secondary Endpoints

- 3.4.1 Proportion of patients alive and free from progression (ie, CR, PR, or SD) per unidimensional irRC and, if brain metastases are present, per iRANO criteria at 24 weeks following SRT
- 3.4.2 Proportion of patients with treatment response (ie, CR, PR, or SD) at irradiated tumor sites at 24 weeks following SRT (refer to Section [10.1](#) for response criteria)
- 3.4.3 Proportion of patients with treatment response (ie, CR, PR, or SD) at non-irradiated tumor sites at 24 weeks following SRT (refer to Section [10.1](#) for response criteria)
- 3.4.4 Proportion of patients who are alive at 2 years after completion of SRT
- 3.4.5 Adverse events including the following:
  - All SRT-related and immunotherapy-related  $\geq$  grade 3 adverse events per the most current National Cancer Institute (NCI) Common Terminology Criteria for Adverse Events Version 5.0 (CTCAE v5.0) occurring from initiation of SRT until 8 weeks after the last SRT fraction
  - All immunotherapy-related adverse events (AEs) occurring from 8 weeks post-SRT until 2 years post-SRT requiring discontinuation of PD-1 or PD-L1 inhibiting therapy and concurrent initiation of immunosuppressive agents such as steroids as described in Section [8.5.2](#).

- 3.4.6 Radiobiological signature as described in Section [1.9.3](#) using blood samples collected prior to SRT (baseline), prior to the 2nd SRT fraction, immediately following completion of SRT (on same day); and at 8, 24, and 52 weeks following completion of SRT

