#### 8.5.2 After 8 Weeks Post-SRT

Only AEs requiring that the PD-1 or PD-L1 inhibitor be discontinued **and** that steroids be administered will be recorded beginning after the 8-week post-SRT AE assessment.

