**Table 5 Footnotes:**

- A. Within +/- 1 week.
- B. Within +/- 2 weeks.
- C. Within +/- 4 weeks.
- D. Assessment and reporting limited to AEs that required discontinuation of the PD-1/PD-L1 inhibitor **and** steroid management.
- E. AEs will continue to be assessed every 2-6 months through end of year 2 in those who continue on PD-1 or PD-L1 inhibitor therapy in accordance with Section [6.7](#).
- F. Refer to Section [6.5.3](#).
- G. Serum chemistry includes the following panels and tests: basic metabolic panel (sodium, potassium, carbonate, chloride, glucose, calcium, BUN, and creatinine); hepatic panel (ALT, AST, ALP, total bilirubin, direct bilirubin, albumin, and total protein).
- H. After week 4, labs are done as part of routine care assessments, and these lab values are not required to be entered in eCRFs. They will be reviewed as part of AE assessments and, as applicable, AE eCRF entry.
- I. For WCBP, the pregnancy test must be repeated if the pre-entry test was performed more than 14 days prior to initiation of SRT. If required, either a urine or serum qualitative pregnancy test may be performed.
- J. The imaging (and/or clinical assessment) used at baseline should be used at each subsequent time point; refer to Section [10.1](#) for information regarding the response criteria to be used. For patients with brain metastasis receiving SRS, disease assessment includes documentation of neurologic status and dosing history of steroids used for CNS edema management.
- K. A goal of imaging at 8 weeks post-SRT is to rule out progressive disease.
- L. Imaging findings at the 24-week time point will be used for analysis of the primary endpoint (Section [13.3](#)). Refer to Section [10.3](#) regarding central review requirements. An optional disease assessment may be done at approximately 28 weeks (at least 4 weeks after the 24-week disease assessment) if needed to confirm response status.
- M. In the absence of post-SRT disease progression, continue with imaging and disease assessment every 2-3 months until 12 months following completion of SRT.
- N. In the absence of post-SRT disease progression, continue with imaging every 2-6 months until 2 years following completion of SRT. (If the patient has initiated a new cancer treatment, imaging is no longer required.)
- O. If the patient is available and willing to have a final blood sample collected for the correlative studies.

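### A non-serious grade 1-2 immunotherapy-related event that ends the inhibitor and needs steroids within 8 weeks of SRT falls in neither safety endpoint, although the same event later is counted

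*Combined protocol and SAP*

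**What the plan says.** Objective 2.2.5 is to assess the toxicity of the study treatment. Endpoint 3.4.5 serves it with two bullets, and the capture rules in Sections 6.7.1 and 8.5 follow the same split at 8 weeks after the last SRT fraction (called week 8 below).

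**Up to week 8**
- Section 8.5.1: "All SRT-related and immunotherapy-related ≥ grade 3 AEs will be recorded beginning at the time of the first SRT fraction", continuing to 8 weeks after SRT.
- Section 6.7.1.1 carries the same threshold, at or above grade 3, and the same end: "grade 3 AEs will continue through 8 weeks following the last SRT fraction".
- Endpoint 3.4.5, first bullet: SRT-related and immunotherapy-related events of grade 3 or higher, "occurring from initiation of SRT until 8 weeks after the last SRT fraction".

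**After week 8**
- Section 8.5.2: "Only AEs requiring that the PD-1 or PD-L1 inhibitor be discontinued and that steroids be administered will be recorded". No grade is named.
- Endpoint 3.4.5, second bullet: "All immunotherapy-related adverse events (AEs) occurring from 8 weeks post-SRT until 2 years post-SRT requiring discontinuation of PD-1 or PD-L1 inhibiting therapy", together with immunosuppressive agents such as steroids. No grade is named here either.
- Table 5, footnote D (weeks 16, 24 and 52): "Assessment and reporting limited to AEs that required discontinuation of the PD-1/PD-L1 inhibitor and steroid management".

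**Related information collected at any time**
- Section 6.6: "The reason for discontinuation of study treatment must be documented in the source documents and in the OnCore database".
- Section 6.5.3 sends oral and parenteral steroids to the eCRF.
- Section 8.6 requires each serious AE (SAE) to have a matching routine AE entry, and the definition in Section 8.1.2 has no grade threshold.

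**The concern.** At week 8 the rule changes from how severe an event is to what it led to. Either rule is reasonable alone. The difficulty is that the second is not also applied to the first period, so an event can be too mild for the early rule and too early for the late one.

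Stopping for an AE does not depend on grade under the protocol. Section 6.6 lists an AE requiring discontinuation, and investigator judgement, without a grade condition, and Section 6.4.5 leaves management of inhibitor side effects to the treating medical oncologist. A grade 2 event that ends the inhibitor is therefore possible.

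At stake is how fully objective 2.2.5 is answered. The first 8 weeks are when radiation and inhibitor are closest together, and so say most about the combination. By counting discontinuation with immunosuppression at any grade later on, the protocol treats that outcome as important. It gives no reason for leaving it out early.

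**Working it through.** The plan states no figure on this point, so there is none to reproduce. The check crosses grade with time for one kind of event: immunotherapy-related, non-serious, ending the inhibitor and needing steroids.

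| | First SRT fraction to week 8 | After week 8, to 2 years |
|---|---|---|
| Grade 3 or higher | Recorded (8.5.1); in 3.4.5, first bullet | Recorded (8.5.2); in 3.4.5, second bullet |
| Grade 1-2 | Not in routine capture (8.5.1, 6.7.1.1); in neither bullet | Recorded (8.5.2); in 3.4.5, second bullet |

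One cell of the four is empty. Three checks bear on its limits.

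1. **Serious events.** A grade 1-2 event that meets the SAE definition gets an SAE entry and a matching AE entry (Section 8.6), so it is in the database. It is still outside both bullets: below the grade limit of the first and before the start of the second.
2. **Purely SRT-related events.** The second bullet of 3.4.5 covers immunotherapy-related events only, and Section 6.7.1.2 limits late assessment in the same way. For a purely radiation-related event there is no later endpoint to compare with. The early-late contrast in the endpoints applies to immunotherapy-related events only.
3. **Other traces.** Sections 6.6 and 6.5.3 capture that the inhibitor was stopped, why, and that steroids were given. They do not require an AE term, grade or attribution. Section 13.4 lists treatment status among the items to be summarised, but for AE rates it names only higher-grade events.

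**Possible size (assumed rates; the documents give none).** Let r be the share of patients with such an early grade 1-2 event, and take n = 42. That is the efficacy-evaluable target in Section 13.2, used only for scale, because no size is given for the safety-evaluable population. Expected uncounted events = n × r; chance of at least one = 1 − (1 − r)^n.

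| r | 42 × r | 1 − (1 − r)^42 |
|---|---|---|
| 1% | 0.42 | 34% |
| 2% | 0.84 | 57% |
| 5% | 2.10 | 88% |
| 6% | 2.52 | 93% |

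With the maximum enrolment of 46, the expected count at 1% to 6% is 46 × 0.01 = 0.46 to 46 × 0.06 = 2.76. Each event is worth 1/42 = 2.4 percentage points on a reported rate.

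**The case against.** The strongest reply is that the information is largely there. Stopping reasons go into OnCore, steroids into the eCRF, serious events into the AE record, and Section 13.4 plans a summary of treatment status. A count of patients who stopped for toxicity from SRT start could be put together. This stands in part: the database is not blind to these patients, and it would be wrong to say the events leave no trace. What is missing is a required AE term, grade and attribution for each, and an endpoint that counts them.

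Section 8.6 opens by saying that all AEs will be recorded in OnCore. In context that names the recording system; Section 8.5 sets the period and grade of capture. On either reading, 3.4.5 still leaves these events out.

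A further reply is that the safety analysis is descriptive, that the protocol cites an established safety profile (Section 3.2), and that the primary endpoint, sample size and two-stage rule are untouched. All of that is true, and it limits the weight of the point.

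A reader might go further and infer that the late rate is biased downward because patients who stopped early stay in its denominator as non-events. The documents do not support this. No denominator is stated for the second bullet beyond the analysis populations. Section 6.7.1.2 ends late AE assessment once the inhibitor is discontinued for any reason, and Table 5 footnote E limits Year 2 assessment to patients still on it, which fits an at-risk denominator at least as well. The bullet is also defined as running from 8 weeks to 2 years and does not claim to be cumulative from SRT start.

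**Conclusion.** The gap is real and follows directly from the stated rules. A non-serious grade 1-2 immunotherapy-related event before week 8 that ends the inhibitor and needs steroids is outside routine AE capture and outside both bullets of 3.4.5, while the same event after week 8 is counted. As a result, no endpoint gives a rate of treatment-ending immunotherapy toxicity from SRT start to 2 years.

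The size is unknown. Under an assumed 1% to 6% of about 42 patients, 0.4 to 2.5 events would be uncounted. That range illustrates scale and is not an estimate for this trial.

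The conclusion does not extend to purely SRT-related events, does not mean that nothing is collected on these patients, and does not show that the late rate is wrong for the window it defines. It is worth correcting because it concerns the most informative period for objective 2.2.5 and the correction is cheap.

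**What to change.** - **Endpoint 3.4.5, second bullet:** start it at the first SRT fraction. One rate of immunotherapy-related AEs requiring inhibitor discontinuation and immunosuppressive agents such as steroids, at any grade, then runs to 2 years. Name the safety-evaluable population (Section 13.5.1) as its denominator.
- **Endpoint 3.4.5, first bullet:** leave it unchanged as a rate of grade 3 or higher events. Adding early treatment-ending events of lower grade here as well would count them in both bullets and blur the severity rate.
- **Sections 8.5.1 and 6.7.1.1:** add that, before week 8, AEs of any grade meeting the discontinuation-plus-immunosuppression criterion are also recorded, with term, grade and attribution.

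A single window also settles a question the text leaves open: where to place an event that begins before week 8 and leads to discontinuation afterwards. One limit remains. Section 13.5.1 requires an inhibitor dose after SRT, so a patient whose inhibitor is stopped for toxicity before that dose would still be outside the rate and is best listed separately.

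The cost is protocol wording and a few extra AE entries. AE assessment is already scheduled during SRT and at weeks 4 and 8 (Table 5), and stopping reasons and steroid use are already collected. The reported toxicity rate may be slightly higher. Sample size and treatment are unaffected.

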## 6.2 Summary of Study Treatment

- Patients will receive a standard treatment regimen of SRT (refer to Section [6.3](#)). The term SRT encompasses all radiotherapy using a stereotactic setup, both stereotactic radiosurgery (SRS) for metastatic lesions in the brain and stereotactic body radiotherapy (SBRT) for SRT delivered to all other locations. Registered patients will be designated as belonging to subgroups as follows:
  - A. Patients receiving SBRT (body) irradiation only
  - B. Patients receiving SBRT and SRS (body and brain) irradiation
  - C. Patients receiving SRS (brain) irradiation only
- The same PD-1 or PD-L1 inhibitor that the patient was receiving prior to study registration will be continued after study registration. The PD-1 or PD-L1 inhibitor will be administered after the last SRT fraction (on the same day) and will continue to be given according to the schedule the patient was receiving prior to study registration through 52 weeks after the last SRT fraction. At the investigator's discretion, administration of the PD-1 or PD-L1 inhibitor may continue during Year 2 or longer (refer to Section [6.4](#) for additional scheduling information).
- At the treating medical oncologist's discretion, one dose of PD-1 or PD-L1 inhibitor may be given after study registration but prior to receiving SRT.
- All doses of the PD-1 or PD-L1 inhibitor administered after study registration will be given at the VCU Massey Cancer Center.

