**Table 1. Expedited Reporting Requirements**

SAEsA	UPsB
Principal InvestigatorC [name] [REDACTED]	Principal InvestigatorC [name] [REDACTED]
Study TeamC [name], BSN [REDACTED]	Study TeamC [name], BSN [REDACTED]
	DSMCD [REDACTED]
	IRBE

A. Refer to Section 8.1.2 for SAE definition. After the 8-week post-SRT assessment, only AEs meeting the criteria outlined in Section 8.5.2 will be recorded; if the AE is an SAE, the event will be reported in an expedited manner as noted on this table.
 
B. Refer to Section 8.1.3.
 
C. Report event within 1 business day of becoming aware of the occurrence.
 
D. Report event within 2 business days of becoming aware of the occurrence.
 
E. Report each UP to the VCU IRB within 5 business days of becoming aware of the occurrence.
	

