**Table 4. Study Calendar – Screening Requirements**

Tests, Exams, and Other Requirements	Prior to Study Registration
Informed Consent	Prior to study-specific procedures
Medical/Surgical History A	Within 28 days
Demographics	
Tumor Imaging B	
Disease Assessment C	
Radiation Oncology Consultation D	
Medical Oncology Consultation E	
Concurrent Medications F	Within 14 days
Baseline Conditions and Symptoms	
Baseline Assessment of prior and ongoing PD-1/PD-L1-related AEs G	
Physical Exam	
Height and Weight	
Vital Signs including BP	
Performance Status ( Appendix 1 )	
CBC with Differential; Platelets	
Serum Chemistry H	
Pregnancy Test I	

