- P. SRT must be administered by VCU Radiation Oncology and must begin within 4 weeks following study registration; refer to Section [6.3](#) for additional SRT requirements and instructions.
- Q. If one dose of the PD-1 or PD-L1 inhibitor needs to be given after study registration (before the first SRT fraction), the pre-SRT dose (if given) must be timed so that the next dose is given on the same day as the last SRT fraction.
- R. At the discretion of the treating medical oncologist, the PD-1 or PD-L1 inhibitor may continue to be administered after 52 weeks following completion of SRT if there has not been disease progression following SRT.
- S. For patients with post-SRT disease progression, follow-up can be limited to assessment of vital status until 2 years after completion of SRT.

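### The adverse-event capture rules do not line up: the changeover at 8 weeks is a fixed day in some sections and a visit in others, and routine recording opens after an on-study inhibitor dose is already allowed

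*Combined protocol and SAP*

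**What the plan says.** **End of the broad window.** Three places fix it at 8 weeks after SRT. Section 8.5.1 says that related grade 3 or higher "AEs will be recorded beginning at the time of the first SRT fraction and continuing until 8 weeks following completion of SRT". Endpoint 3.4.5 counts such events "occurring from initiation of SRT until 8 weeks after the last SRT fraction". Section 6.7.1.1 says that assessment and reporting of grade 3 or higher "AEs will continue through 8 weeks following the last SRT fraction". Endpoint 3.4.5 also starts its late-event component at the same fixed 8 weeks.

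**Start of the narrow rule.** Under Section 8.5.2, events that require both stopping the inhibitor and giving steroids "will be recorded beginning after the 8-week post-SRT AE assessment". Table 1 note A uses the same visit-based trigger: "After the 8-week post-SRT assessment, only AEs meeting the criteria outlined in Section" 8.5.2 are recorded. Table 5 note B gives the week-8 visit a window of 2 weeks either side. Table 5 note D limits the AE checks at weeks 16, 24 and 52 to the narrow rule.

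**Opening edge.** Section 6.2 allows that "one dose of PD-1 or PD-L1 inhibitor may be given after study registration but prior to receiving SRT". Table 5 note P says that SRT "must begin within 4 weeks following study registration". Table 4 places the "Baseline Assessment of prior and ongoing PD-1/PD-L1-related AEs" before registration. In Table 5 the AE row has no entry in the On Study column, and its first entry is during SRT.

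**The concern.** Toxicity is secondary objective 2.2.5, and endpoint 3.4.5 is where it is reported. That endpoint depends on two rules meeting at one point in time, and on recording being open whenever on-study treatment is given. Neither condition is met.

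At the closing edge, site staff cannot follow 8.5.1 and 8.5.2 together unless the visit falls exactly on day 56. After an early visit, 8.5.1 requires every related grade 3 or higher event to be recorded until day 56, while 8.5.2 says that only the narrow class is recorded. The next scheduled AE check, at week 16, is limited to the narrow class. Events that belong to endpoint 3.4.5 can therefore go unrecorded.

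At the opening edge, Section 2.2 defines study treatment as SRT plus the inhibitor. One component may be given on study before routine recording of its related events opens. There is no control arm to show the background rate of immune events. A check immediately before SRT is thus the main protection against attributing a pre-existing event to the combination.

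**Working it through.** The plan states no figure to reproduce here; this is calendar arithmetic on its own time limits.

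**Closing edge.** Inputs: broad rule ends on day 56 after the last fraction (3.4.5, 6.7.1.1, 8.5.1); narrow rule starts at visit day V (8.5.2, Table 1 note A); V runs from 42 to 70 (Table 5 note B, 8 weeks plus or minus 2).

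- Days under both rules, which conflict = max(0, 56 − V)
- Days under neither rule as worded = max(0, V − 56)

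| Visit day V | Conflict (days) | Neither rule (days) |
|---|---|---|
| 42 (week 6) | 14 | 0 |
| 49 | 7 | 0 |
| 56 (week 8) | 0 | 0 |
| 63 | 0 | 7 |
| 70 (week 10) | 0 | 14 |

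The two cases differ in consequence. After an early visit, the next scheduled check is week 16 and note D narrows it, so a related grade 3 event in days 42 to 56 that did not need both discontinuation and steroids has no scheduled check that would collect it. With a late visit, the week-8 check carries no note D restriction, so staff may well pick up events from days 56 to 70. The text, however, gives no recording rule for those days, although the late component of 3.4.5 has already started.

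**Opening edge.** Inputs: registration to first fraction, at most 28 days (6.3.3, Table 5 note P); baseline AE assessment within 14 days before registration (Table 4, as the table reads in extracted form); the dose after a pre-SRT dose must fall on the last SRT day (6.4.3, Table 5 note Q).

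- Longest time from baseline assessment to fraction 1 = 14 + 28 = 42 days. This is time since baseline, not time on study treatment.
- Longest on-study time before routine recording = 28 days.
- Lead of the optional dose over fraction 1 = min(28, I − S), not below 0, where I is the dosing interval and S the days from first to last fraction.

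The documents give no dosing intervals. Under assumed intervals, with S of 7 to 14 days:

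| Assumed I (days) | Lead of pre-SRT dose (days) |
|---|---|
| 14 | 0 to 7 |
| 21 | 7 to 14 |
| 28 | 14 to 21 |
| 42 | 28 (capped) |

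The full 28 days needs I of at least 28 + S, that is 35 days for S = 7 and 42 days for S = 14. Section 6.4.3 permits schedule modifications, so these are typical values rather than limits.

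**Effect on a rate.** If the safety denominator were about the 42 evaluable patients (an assumption), one misclassified patient would move a rate by 1/42 = 2.4 percentage points.

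**After alignment.** With recording from registration and one fixed day 56, the 28-day and 14-day maxima both become 0. No sample size or error rate changes.

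**The case against.** The strongest reply is that the endpoint itself is sound. Section 3.4.5 fixes both sides of the changeover at 8 weeks, so a reader who infers that grade 3 or higher capture ends at a floating visit goes too far: 8.5.1, 6.7.1.1 and 3.4.5 all end it on a fixed day. What floats is the start of the narrow rule. Nor does a week-10 visit lengthen the broad window; it leaves a gap after it. Both corrections stand. The contradiction remains, because collection is governed by 8.5.2 and Table 5 note D, and an endpoint cannot count events that were not collected.

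On the opening edge, the optional dose continues a drug the patient already takes, and SRT is what the trial adds. Opening routine capture at fraction 1 is therefore a defensible choice, and the 28 days is an outer limit on an optional dose. This too has weight. But the endpoint covers immunotherapy-related events as well, and Section 4.1.3 requires an inhibitor dose within 60 days before registration. Immune events can thus emerge between baseline and fraction 1 with or without the optional dose.

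A reader might also infer that serious events before SRT carry no recording or reporting duty. The documents do not support that. Section 8.6 and Table 1 give no start date, and the only restriction in Table 1 applies after the 8-week assessment. Section 6.6 requires the reason for stopping study treatment to be documented. The duty before SRT is undefined in its start, not excluded. Section 8.6 also wants a matching routine entry for each SAE, which 8.5.1 does not provide for before fraction 1.

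Finally, a patient whose event prevents SRT is outside the safety population under 13.5.1, whenever recording begins. Earlier recording alone would not bring that patient into the analysis.

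**Conclusion.** The point holds at both edges, more firmly at the closing one. The sections disagree on when the narrow rule begins, by up to 14 days in either direction. An early visit can leave endpoint 3.4.5 short of events from days 42 to 56, and a late one leaves days 56 to 70 without a rule as worded.

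At the opening edge, non-serious related grade 3 or higher events in an interval of at most 28 days fall outside the routine record. For events that follow the optional dose, the interval is usually shorter. That an event still present at fraction 1 would be attributed to the combination is an inference from the missing check, since no text dates events by visit or reassigns earlier onsets. The documents do not show that events are misdated. Setting the 42 days since baseline against the 56-day follow-up would compare unlike periods and should not be used as a measure of loss.

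The effect is confined to a descriptive secondary safety summary; the primary endpoint and the Simon decision rule are untouched. The conclusion assumes that Tables 4 and 5 were read correctly from the extracted layout. The dose lead times rest on assumed intervals. It should be corrected, but it does not threaten the main result.

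**What to change.** 1. In 8.5.2 and Table 1 note A, replace the visit-based changeover with day 56 after the last fraction, as 3.4.5, 6.7.1.1 and 8.5.1 already imply. For visits held before day 56, ask about the remaining days at the next contact and exempt that question from Table 5 note D.
2. In 8.5.1, 3.4.5 and Table 5, open recording of related grade 3 or higher AEs and of SAEs at registration, or at the first on-study inhibitor dose. Add an AE check before fraction 1, when the pre-SRT blood sample is drawn.
3. Report pre-SRT events separately from those arising after SRT begins, and list registered patients who do not reach SRT, because 13.5.1 leaves them out of the safety population.

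The cost is protocol wording, one extra AE check alongside a blood draw that is already planned, and a few more AE records. No treatment rule, sample size or primary analysis changes.
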